4.8. The Lan-DeMets Error Spending Function

In case any additional interim analyses are requested by the IDSMC, the flexible Lan-DeMets (Lan and DeMets, 1983) type I error spending function analog of the O'Brien-Fleming boundaries will be used to monitor the primary endpoint as a guide for the IDSMC for an overall two-sided type I error rate of 0.05 based on a two-sided test. This is defined as follows. If we let n denote the sample size according to the calculation for the planned study and n_o denote the number of individuals at an interim analysis, then let $t = n_o/n$. This "O'Brien-Fleming" error spending function has the form

$$\alpha(t) = 2 - 2\Phi(Z_{\alpha/2}/\sqrt{t})$$

where $Z_{\alpha/2} = 1.96$ reflects the critical value corresponding to the analysis that would be done for an analogous trial with a fixed sample size and a two-sided test (Lans and DeMets, 1983). For the interim analysis planned when 50% of the sample will be available $t = 1/2$ and we obtain

$$\alpha(1/2) = 2(1 - \Phi(Z_{\alpha/2}/\sqrt{0.5})) = 0.005573$$

as the threshold for significance and stopping at the interim analysis. This constitutes a conservative stopping rule which we will adopt to preserve much of the type I error for the analysis at the conclusion of the study, to minimize the bias in estimates of the treatment effect from sequential trials, and to gear the trial towards one that will be large enough to answer the several important secondary questions we aim to address including the effect of neutralizing antibodies.

4.9. Interim Calculation of Conditional Power for Futility

Conditional power will be presented as an additional guide to the IDSMC for the primary outcome based on a test for the difference in two binomial proportions (Jennison and Turnbull, 2000). Conditional power allows computation of the probability of obtaining a statistically significant result by the end of the trial given the data accumulated thus far, incorporating a hypothesized treatment effect (e.g., the treatment effect assumed for sample size determination) thereafter. If the conditional power is less than 20% under the original trial assumptions, consideration could be given to stop the trial. An unblinded independent statistician will prepare the reports for IDSMC to review when making their recommendations.

The interim analysis report will be created by an independent statistician who will have access to the randomization code.

4.10. Sample Size Re-Estimation

There is uncertainty about the intubation and mortality rate that will be observed in this study due to possibly evolving profile of COVID-19 patients admitted to hospital over the course of the pandemic. To address this, a blinded sample size re-estimation will take place when the primary outcome is available for 50% of the target sample, which coincides with the time of the interim analysis report. Sample size will be adjusted if the estimated event rate is different from that originally specified to the extent that the study is not expected to achieve the desired nominal power for the test of the primary outcome. Friede and Kieser (2004) give the following formula for total sample size re-estimation: We let $n = n_e + n_s$ denote the total sample size where n_e and n_s denote the number of individuals in the experimental (CCP) and standard of care arms respectively, and let θ denote the randomization ratio where $n_s = \theta n_e = 0.5n_e$. We let d be the absolute risk difference we wish to detect (which was specified in the original sample size calculation). Then if we observe a pooled composite event rate p , then

$$n = n_e + n_s = \left(2 + \theta + \frac{1}{\theta}\right) \frac{(Z_{\alpha/2} + Z_{\beta})^2}{\delta^2} p(1 - p),$$

gives the revised total sample size.

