12. STATISTICAL CONSIDERATIONS

12.1. Sample Size Considerations

Assuming a baseline risk of intubation or death by Day 30 of 30% in hospitalized patients with standard of care, a sample size of 1200 (800 in the CCP arm, and 400 in the standard of care arm) would provide 80% power to detect a relative risk reduction of 25% with CCP therapy using a 2-tailed test at level α = 0.05. This assumes no patient is lost to follow-up. Lost follow-up is expected to be minimal.

There is uncertainty about the intubation and mortality rate that will be observed in this study due to possibly evolving profile of COVID-19 patients admitted hospital over the course of the pandemic. To address this, a blinded sample-size re-estimation will take place when the primary outcome is available for 50% of the target sample. Sample size will only be adjusted if the estimated event rate is different than the originally specified event rate to a sufficient extent that the study is not expected to achieve the desired nominal power for the test of the primary outcome.

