1.3. Sample Size Justification

Assuming a 30% risk of the composite outcome of intubation or death by Day 30 among hospitalized patients under standard of care, a sample size of 1200 individuals (800 in the CCP arm, and 400 in the standard of care arm) will provide 80% power ($\beta = 0.20$) to detect a relative risk reduction of 25% with CCP therapy using a 2-tailed test at level $\alpha = 0.05$. We assume that no patient will be lost to follow-up.

2. Responses

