4.2. Analysis of Primary Outcome

If we let p_e and p_s denote the probability of the composite outcome (intubation or death at Day 30) for the experimental (CCP) and standard of care arms respectively, then the null and alternative hypotheses are $H_0: p_e = p_s$ and $H_1: p_e \neq p_s$, respectively. The probability of intubation or death between randomization and Day 30 will be estimated for each treatment group by the proportion of individuals randomized to each group who required ventilation or died by Day 30. The primary analysis will be based on a 2-sided Wald test of the null hypothesis that probability of intubation or death is the same among individuals receiving CCP or standard of care. The percent relative risk reduction, defined by $100(1 - p_e/p_s)$, will be estimated along with a 95% confidence interval.

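### The blinded sample-size re-estimation fixes an absolute risk difference although the trial is powered for a 25% relative reduction, so it moves the sample size in the wrong direction when the event rate changes.

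*SAP*

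**What the plan says.** Protocol 12.1 sets the design: "Assuming a baseline risk of intubation or death by Day 30 of 30% in hospitalized patients with standard of care", 1200 patients randomised 2:1 "would provide 80% power to detect a relative risk reduction of 25% with CCP therapy", two-sided alpha 0.05. SAP 1.3 repeats the target: "to detect a relative risk reduction of 25% with CCP therapy". Neither section states an absolute difference. The effect measure for the primary outcome in SAP 4.2 is also relative: "The percent relative risk reduction, defined by" 100(1 − p_e/p_s).

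Both documents plan a blinded re-estimation once the primary outcome is known for half the target sample, because the event rate is uncertain. Both change n only if the observed rate means that nominal power is not expected. SAP 4.10 supplies the formula and describes its effect size thus: "We let d be the absolute risk difference we wish to detect (which was specified in the original sample size calculation"). It gives no value for d (written δ in the formula; I read the two as the same) and no instruction to recompute it at the observed rate.

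**The concern.** The 7.5-point difference follows only from taking 25% of an assumed 30% control risk, and that risk is exactly what the re-estimation treats as unknown. If the risk turns out different, a 25% relative reduction is no longer 7.5 points. Holding 7.5 points fixed changes the target effect without saying so.

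The direction of the adjustment also reverses. With d constant, n is proportional to p(1 − p), which rises with p below 50%. With the relative risk constant, d is proportional to p, so n is proportional to (1 − p)/p, which falls as p rises. The purpose of this step is to protect power against an unexpected event rate. If it moves the wrong way, the trial can finish underpowered for its stated effect with the re-estimation reporting no problem, or can recruit patients it does not need. Protocol 11.10 also lists an infeasible revised sample size as a possible ground for termination, so at a high event rate that judgement could rest on an inflated number.

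**Working it through.** **Inputs.** Control risk 0.30, relative reduction 25%, two-sided alpha 0.05, power 80%, 800 CCP and 400 standard of care, no loss to follow-up (Protocol 12.1, SAP 1.3). Formula and θ = 0.5 from SAP 4.10. The value d = 0.30 − 0.225 = 0.075 is derived; it is not stated in either document.

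**Step 1: reproduce the design.** A two-proportion calculation with pooled variance under the null, 0.30 against 0.225 at 2:1, gives 400 + 800 = 1200 with 80.1% power. The stated sample size is correct.

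**Step 2: the SAP 4.10 formula at the design point.** The pooled rate is (0.30 + 2 × 0.225)/3 = 0.25.

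n = (2 + 0.5 + 2)(1.96 + 0.8416)² × 0.25 × 0.75 / 0.075² = 1177

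This is within 3% of 1200, so the formula is sound at the design rate.

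**Step 3: the difference implied by a 25% relative reduction.** Under 2:1 allocation and relative risk 0.75, p = (p_s + 2 × 0.75 p_s)/3 = (2.5/3)p_s. Hence p_s = 1.2p and d = 0.25 × 1.2p = 0.30p.

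**Step 4: compare the two rules.** Both n columns use the SAP 4.10 formula. Power is for 800 against 400 at relative risk 0.75, pooled-variance test.

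| Pooled p | Control risk (1.2p) | n, d = 0.075 | n, d = 0.30p | Power at 1200 for a 25% reduction |
|---|---|---|---|---|
| 15% | 18% | 801 | 2224 | 54% |
| 20% | 24% | 1005 | 1570 | 68% |
| 25% | 30% | 1177 | 1177 | 80% |
| 30% | 36% | 1319 | 916 | 89% |

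The two rules agree only at the design rate. The two-proportion calculation of Step 1 gives 2277, 1602, 1200 and 930 in place of the d = 0.30p column, so the pattern does not depend on which sample-size formula is used.

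**Step 5: the effect that fixed d targets.** With d = 0.075 and 2:1 allocation, p_s = p + (2/3) × 0.075 = p + 0.05. At p = 20% the target becomes 0.075/0.25 = a 30% relative reduction; at p = 15% it becomes 0.075/0.20 = 37.5%.

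**Step 6: apply the adjustment condition.** At pooled 20%, power at 1200 for a fixed 7.5-point difference (25% against 17.5%) is 86%, so no increase is triggered although power for a 25% reduction is 68%. At pooled 30% (35% against 27.5%) it is 76%, so an increase of 1319 − 1200 = 119 is triggered although power for a 25% reduction is already 89%.

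**The case against.** **n would probably not be cut.** Because n is adjusted only when power looks inadequate, a low event rate would most likely leave it at 1200. That is right, and it defines the harm: at low rates the fault is a missed increase. Step 6 shows that the condition does not rescue the rule, since it is judged against the wrong effect in both directions.

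**A fixed absolute target can be legitimate.** A 30% control risk and a 25% reduction do fix one absolute difference, and SAP 4.9 bases conditional power on a difference between proportions. A sponsor may choose a constant 7.5 points. But no section says that the target changed from relative to absolute, and the only stated target and the reported measure are both relative. The statement that more patients are needed at low rates is conditional on the relative target remaining in force.

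**The IDSMC can review the result.** SAP 4.11 says that the committee and the unblinded statistician will be able to judge the revised target. That is a check, but it supplies no corrected formula, and a decision not to increase n produces no revised target to question.

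**The sizes are illustrative.** The documents give no expected range of event rates, and at pooled 20% the loss, from 80% to 68%, is material but not extreme. The SAP names a Wald test; with unpooled variance, power at 1200 is about 66% at pooled 20% and 51% at pooled 15%, slightly worse than tabulated.

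The primary test, the type I error rate and the planned 1200 are not affected.

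**Conclusion.** The concern holds. SAP 4.10 rests on an absolute difference that the original calculation did not state, and it fixes that difference where the stated target requires it to move with the event rate. For a 25% relative reduction, the formula understates the required n by about 565 at pooled 20% (1570 − 1005) and about 1423 at pooled 15% (2224 − 801), and overstates it by about 403 at pooled 30% (1319 − 916). This should be corrected before the re-estimation is run, because the rule can determine the final sample size and its purpose is to protect power. The conclusion assumes that the 25% relative reduction remains the target, that d means the implied 7.5 points, and that allocation is 2:1.

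**What to change.** In SAP 4.10, replace the fixed difference with one derived from the blinded pooled rate: relative risk held at 0.75, p_s = 1.2p, d = 0.30p, used in the same formula. Judge whether nominal power is expected against that d as well. If the resulting n is infeasible, a case Protocol 11.10 already foresees, keep 1200 and report the power for a 25% relative reduction at the observed rate.

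State in the text that p_s = 1.2p assumes the design effect, as is usual in blinded re-estimation. If plasma had no effect and both arms were at 30%, the rule would read the control risk as 36% and return 916.

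If a constant 7.5-point target is truly intended, the alternative is to state and justify it, give its value, and remove the claim that it was originally specified.

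The cost is one line of SAP text. No new data are needed and blinding is unaffected. The revised n, or the restated power, may be less favourable if the event rate is low.

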4.11. Conventions Regarding Blinding

It is generally recognized that blinding of the investigators to the arm-specific data is desirable during the course of a clinical trial. The monthly safety reports being prepared for the IDSMC will display data on trial conduct aggregated across centers and specific to each center, and will give unblinded safety data in order to equip them to assess safety.

At the point of the interim analysis being conducted when 50% of the target sample size can provide primary outcome data, again the data will be presented with the randomized treatment arm clearly specified in order to equip the IDSMC with the information needed to interpret the results of the interim analyses.

A blinded version of the monthly Progress and Safety Report will be created for the Executive Committee in which the data will only be presented in such a way that the treatment arm cannot be identified; this will be achieved by using generic labels A and B for the two arms, not reporting the sample sizes for these groups, and reporting simply the percentages of individuals experiencing particular events, averages, and standard deviations rather than standard errors for continuous variables. For some features data will only be presented in aggregate form.

The sample size re-estimation will be conducted by a blinded investigator ([name]) based on data aggregated across the two arms as described in Sections 4.9. The rationale is that this calculation is the responsibility of the investigators and the investigators ideally remain blinded to the interim outcomes.

As the independent statistician preparing the interim analysis report is unblinded and the IDSMC members are unblinded, they will be equipped to assess the suitability of the revised target sample size.

5. References

- Friede T and Kieser M (2004). Sample size recalculation for binary data in internal pilot study designs. *Pharmaceutical Statistics*, 3: 269-279.
- Jennison C and Turnbull BW (2000). *Group Sequential Methods with Applications to Clinical Trials*. Chapman and Hall, Boca Raton.
- Kalbfleisch JD and Prentice RL (2011). *The Statistical Analysis of Failure Time Data (Vol. 360)*. John Wiley and Sons.

1 LABORATORY MARKERS TO BE EXAMINED AS POSSIBLE EFFECT MODIFIERS

Here we give a clear description of the markers under consideration that are measured in the convalescent plasma transfused in the CCP arm of CONCOR-1.

1.1 ANTI-RBD TOTAL IG AS MEASURED BY ELISA

This marker is reported as the optic density (O.D.), which is a measure directly proportional to the amount of antibody. This is recorded into the REDCap database directly.

1.2 ANTI-SPIKE IGG AS MEASURED BY FLOW CYTOMETRY

This marker is reported as the mean fluorescence intensity (MFI), which is directly proportional to the amount of antibody. This is recorded in the REDCap database directly.

1.3 PLAQUE REDUCTION NEUTRALIZATION TITER 50% (PRNT50)

This marker is reported as the highest titer at which the plasma still inhibits at least 50% of viral entry in cells in a plaque reduction assay. Titers are determined by doubling the dilution at each stage, leading to discrete values ranging from 1:20 to $\geq 1:640$ (or $\geq 1:1280$ for some plasma samples tested at the beginning of the pandemic). Before uploading into REDCap:

- Left-censored values will be dealt with via mid-point imputation so if 50% of the viral entry in cells is not inhibited at the first dilution, then the value is taken as 1 : 10 where 10 is halfway between 0 and 20.
- Right-censored values were changed as follows:
 - If it was determined that 50% of the cells were inhibited at at the highest dilution of 640 (i.e. we know it is $\geq 1:640$), the value was taken to be 1:640
 - If it was determined that 50% of the cells were inhibited at at the highest dilution of 1280 (i.e. we know it is $\geq 1:1280$), the value was taken to be 1:1280
- Ultimately the dilution rate was inverted to express titers in terms of the number of dilutions so a titer of 1:40 was expressed as 40 dilutions

1.4 ANTIBODY-DEPENDENT CELL CYTOTOXICITY (ADCC)

This marker is reported as the proportion of the target cells that were killed by NK cells in presence of the antibody. Before uploading in REDCap the ADCC proportion X was re-expressed as the ADCC ratio to give $Y = X/(1 - X)$ (e.g. a value of 66% was expressed as 2 corresponding to a 66.66:33.33 = 2:1 ratio).

1.5 COMBINING ANTIBODY DATA FROM TWO PLASMA UNITS

1.5.1 DEALING WITH REPLICATE MEASUREMENTS ON A GIVEN PLASMA UNIT

When multiple samples from the same donor plasma have been tested, the mean result was uploaded in REDCap. For the ADCC marker the averaging will be carried out on the scale of the proportion and then the ratio will be computed based on this average proportion.

1.5.2 COMBINATION OF TEST RESULTS FROM DIFFERENT PLASMA UNITS

All test values are entered into REDCap are measures of concentrations expressed on an absolute scale. Test results from the two different plasma units transfused to an individual will be combined as follows. A weighted sum of the two concentrations will be computed with weights based on the volume of the respective units. That is, we will compute an estimate of the “total antibody dose” for the pooled sample as

$$\text{Total Dose} = (\text{Vol. 1} \times \text{Conc. 1} + \text{Vol. 2} \times \text{Conc. 2})$$

EXAMPLE: Consider two units and the anti-RBD ELISA results with the first 235 ml having an O.D. of 0.25, and the second unit of 240 ml having an OD of 1.06. The overall OD is computed as

$$\text{Total Dose} = 235 \times 0.25 + 240 \times 1.06 = 313.15$$

This patient would be considered to have received the equivalent total dose of antibodies corresponding to a 500 ml plasma transfusion with an anti-RBD antibodies at $313.15/500 = 0.63$ optical density.

1.6 LOG TRANSFORMATION BEFORE ANALYSIS

Final marker values representing concentrations will be log-transformed (\log_{10}) before being entered in statistical analysis assessing their pharmacological effect. So with a concentration of 0.63 we will use $\log_{10}(0.63) = -0.20$.

1.7 HANDLING MISSING DATA

1.7.1 MISSING UNIT VOLUMES

When the volume of a plasma unit is missing, the median volume of convalescent plasma units from the same blood provider will be imputed.

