4.4.1. CCP

Patients will receive approximately 500 mL of CCP (from one single-donor unit of 500 mL or 2 units of 250 mL from one or two donors) collected by apheresis from donors who have recovered from COVID-19 and frozen (1 year expiration date from date of collection). The plasma unit will be thawed as per standard blood bank procedures and infused into the patient slowly over 4 hours or as per local procedures. When administering 2 units of 250 mL, the 2nd unit should be administered immediately after the first unit, and we recommend that it should be given within 12 hours after the first unit. The patient will be monitored for adverse events as per each site's policies. Details regarding the CCP are summarized in Section 5.0.

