5.4.2. Acquisition and Formulation

5.4.2.1. For Canadian Sites

Plasma will be collected by apheresis from qualified donors who have consented to donate, using the equipment and technologies already in operation at Héma-Québec and Canadian Blood Services following standard operating procedures.

Because apheresis collection allows for plasma only collection while blood cells are returned to the donor, donor are eligible to donate every 6 days (at minimum). This will permit the collection of CCP from the same donor at weekly intervals. SARS-CoV-2 antibody titers will be monitored at each donation to ensure the presence of sufficient amounts of antibody for the treatment of patients suffering from COVID-19.

Plasma collection using the TRIMA® Accel™ technology (Terumo BCT)

The TRIMA® Accel™ technology allows the automated collection of different blood components and contains programs for plasma collection only. Disposable sterile kits for plasma collection are available (kits with 3 or 4 plasma bags). Depending on the donor characteristics (calculated blood volume), plasma volumes up to 750 mL can be collected. The procedure starts with the collection of a small volume of blood in a sampling bag; this blood will be used for regulatory analyses at Héma-Québec and Canadian Blood Services (transfusion transmissible diseases) and to establish the anti-SARS-CoV-2 seropositivity. During collection, blood is mixed with ACD-A (anticoagulant citrate dextrose, solution A), plasma is separated from blood cells by centrifugation and collected in 2 or 3 bags (depending on the target volume that has been predefined) based on the estimated total blood volume of the donor whereas blood cells are returned to the donor.

Plasma collection using the PCS®2 technology (Haemonetics)

This automated system is used to collect plasma only. Samples required for regulatory analyses and antibody seropositivity determination are taken directly from the collected unit after plasma collection is completed. During collection, blood is mixed with anticoagulant (sodium citrate 4%) to avoid clotting and centrifuged in a single use, sterile centrifugation bowl to separate plasma from blood cells. When separation is completed, plasma is automatically transferred to the collection bag and thereafter, blood cells are returned to the donor.

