5.8. Dose of CCP

The dose of CCP will be approximately 500 mL. This will be administered as be either 1 unit of 500 mL or 2 units of 250 mL of apheresis CCP.

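### A missing plasma unit volume is filled with the provider's overall median, which may be the wrong unit size if a provider issues both 250 mL and 500 mL units

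*SAP*

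**What the plan says.** The SAP supplement on antibody analyses, section 1.7.1, gives the rule for a unit whose volume is missing: "the median volume of convalescent plasma units from the same blood provider will be imputed". It does not mention unit size or the number of units the patient received.

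Volume matters because of supplement section 1.5.2: "A weighted sum of the two concentrations will be computed with weights based on the volume of the respective units". The sum of volume times concentration is then expressed as the equivalent concentration in 500 mL, and section 1.6 takes log10 before modelling. Section 2 adjusts all the marker analyses for provider as a factor.

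Two unit formats are allowed. Protocol 4.4.1 describes the dose as coming "from one single-donor unit of 500 mL or 2 units of 250 mL from one or two donors", and protocol 5.8 repeats "1 unit of 500 mL or 2 units of 250 mL of apheresis CCP". SAP 1.1 agrees. None of these links a format to a supplier.

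Protocol 5.4.2.1 describes two collection systems for the two Canadian suppliers taken together. In one, "plasma is separated from blood cells by centrifugation and collected in 2 or 3 bags", with up to 750 mL collected. In the other, "plasma is automatically transferred to the collection bag". Sections 5.4.2.2 (United States) and 5.4.2.4 (Israel) describe the same contrast for a single supplier each. Section 5.4.2.3 (Brazil) gives one system only.

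**The concern.** A provider median is a sensible guess when a provider's units are all about the same size. It is a poor one when they come in two sizes that differ twofold. The median then falls on the size that makes up more than half of the units, and each unit of the other size with a missing volume gets the wrong one. Adjusting for provider does not remove the error, because it arises between formats within a provider.

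The dose is the exposure in the supplement's marker models, including the generalized additive models in section 2.2 that are meant to show threshold levels. A patient plotted at half or double the true dose is a false point in that display, and misclassified exposure pulls a marker slope towards zero.

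**Working it through.** **Inputs.** Formats of 500 mL and 250 mL (protocol 4.4.1 and 5.8). Dose formula, 500 mL scaling and worked example (supplement 1.5.2). Log10 scale (1.6). Imputation rule (1.7.1).

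**The plan's own example.** Dose = Vol1 × Conc1 + Vol2 × Conc2 = 235 × 0.25 + 240 × 1.06 = 58.75 + 254.40 = 313.15. Divided by 500 this is 0.63, and log10(0.63) = −0.20. All three figures agree with the supplement.

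**Where the median falls.** It is taken over units, and a two-unit patient contributes two. If a share s of a provider's patients receive one 500 mL unit, the share of its units that are 500 mL is s / (2 − s). This exceeds one half only if s exceeds 2/3. Below that the median is about 250 mL. For example, s = 0.4 gives 0.4/1.6 = 25% of units at 500 mL.

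**Error for one patient, nominal volumes.**

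| Case | Dose ratio, imputed to true | log10 error |
|---|---|---|
| One 500 mL unit imputed at 250 mL* | 250/500 = 0.50 | −0.30 |
| Both 250 mL units imputed at 500 mL | 1000/500 = 2.00 | +0.30 |
| One of two 250 mL units imputed at 500 mL, equal concentrations | 750/500 = 1.50 | +0.18 |
| Same, optical densities 0.25 and 1.06 | 1.19 or 1.81, by which volume is missing | +0.08 or +0.26 |

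*Only if the 500 mL scaling is also applied to a single unit.

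**The supplement's example with volumes imputed at 500 mL.**
- First volume missing: 500 × 0.25 + 240 × 1.06 = 379.40, ratio 1.21.
- Second missing: 235 × 0.25 + 500 × 1.06 = 588.75, ratio 1.88.
- Both missing: 500 × (0.25 + 1.06) = 655.00, ratio 2.09, an equivalent optical density of 1.31 instead of 0.63. The ratio slightly exceeds 2 because the true volumes are below 250 mL.

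**The same example with format-specific imputation at 250 mL.** The doses are 316.90, 323.75 and 327.50, with ratios 1.01, 1.03 and 1.05. The log10 error is at most 0.02.

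**Effect on a slope, as illustration only.** The documents give no rates. Assume s = 0.4, volumes missing at random in a proportion m, an SD of log10 dose of 0.20 to 0.35, and the 500 mL scaling applied to single units. The median is then about 250 mL, so only single-unit patients with a missing volume are wrong, a proportion p = 0.4m, each by −0.301. The slope shrinks by the factor SD² / (SD² + 0.301² × p(1 − p)).
- m = 2%: p = 0.008, added variance 0.0906 × 0.00794 = 0.00072. The factor is 0.04/0.04072 = 0.98 at SD 0.20 and 0.1225/0.12322 = 0.99 at SD 0.35.
- m = 20%: p = 0.08, added variance 0.0906 × 0.0736 = 0.00667. The factor is 0.86 at SD 0.20 and 0.95 at SD 0.35.

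If 0.20 to 0.35 is instead the SD per unit and two-unit patients draw on two independent donors, the dose varies less and the losses are somewhat larger. Simulation of 400,000 patients gave factors of 0.81 to 0.92 at m = 20%.

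**The case against.** The strongest objection is that the mixed-format provider is an inference. Protocol 5.4.2.1 lists two systems for two Canadian suppliers jointly and does not say that either uses both. If each used one, a provider median would already separate the formats. For the United States and Israeli suppliers, which each have two systems, no volume per bag or release format is given, and a single collection bag is not said to be a 500 mL transfusion unit. This stands. The documents leave the situation open and do not establish it.

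Second, the volume-weighted formula appears under a heading about combining two units. Nothing states that a single unit's concentration is multiplied by its volume and divided by 500. This also stands, and it matters: every slope figure above comes from single-unit patients. The doubling of a two-unit dose does not need that step, but it needs a provider with more than two-thirds single-unit patients. The per protocol definition (SAP 3.2) takes two units as the norm and treats a single 500 mL unit as a special case, which does not suggest such a majority.

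Third, volume is a planned supplier data item for every country (protocol 8.1), so substantial missingness should not be presumed. That is fair.

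A reader might infer that each affected patient's dose is wrong by a factor of two, or that the marker slopes are known to be attenuated by a stated percentage. The documents support neither. Twofold is essentially the worst case, and the percentages rest on an assumed format mix, missing rate and spread.

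**Conclusion.** The rule in supplement 1.7.1 ignores unit format although two formats that differ twofold are allowed. If a provider issues both, an imputed volume can be that of the wrong format, and the 500 mL-equivalent dose can be wrong by up to about twofold (0.30 log10). The worst cases are both 250 mL volumes imputed at about 500 mL, or a single 500 mL unit imputed at about 250 mL with the same scaling applied to single units.

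The effect on results cannot be sized from the documents. Under the stated assumptions it is about 2% of a marker slope or less at 2% missing, and larger only if much more is missing. The point is confined to the exploratory antibody analyses. It would be wrong to read it as touching the primary test, the secondary outcomes or safety, none of which uses unit volume. It is a small improvement worth making because it is free.

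**What to change.** In supplement 1.7.1, impute the median volume among units of the same provider **and the same format** (one-unit or two-unit dose). Use the nominal volume of that format, 500 or 250 mL, if too few units are available.

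The format should be that of the dose issued, not the number of units finally transfused. Otherwise a patient whose second 250 mL unit was not given would be classed as a 500 mL recipient. A sentence in 1.5.2 saying whether the 500 mL scaling also applies to a single unit would settle the other open point.

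The cost is one phrase and one sentence in the supplement. The number of units given has to be known already, because the per protocol definition depends on it. Where a provider issues only one format, the revised median rule gives the same value as the present one.
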